4. STUDY POPULATION

4.1. Inclusion criteria

- 1) Signed informed consent
- 2) Blood alcohol level below <0.1‰ (0.1 g/L) at signing informed consent
- 3) 25-70 years of age at screening
- 4) Moderate and severe AUD according to DSM-V (meeting ≥4 out of 11 criteria)
- 5) B-PEth levels of ≥0.5 µmol/L at screening visit (visit 1) as defined by at least 2 HDD per week on a typical week.
- 6) Continuous high alcohol consumption over the last 3 months prior to screening
- 7) Available phone number for contact
- 8) Ability to speak and write in Swedish

4.2. Exclusion criteria

Subjects must NOT enter the study if any of the following criteria are fulfilled:

- 1) Total abstinence between screening and randomization visit
- 2) Treatment of alcohol withdrawal within 30 days of study initiation
- 3) Pharmacological treatment within 3 months of study initiation and during the study period that may affect alcohol consumption, including but not exclusive to, varenicline, bupropion, disulfiram, acamprosate, naltrexone, nalmefene, baclofen, topiramate, ondansetron, mirtazapine, methylphenidate, dexamphetamine, atomoxetine, pregabalin, buprenorphine and methadone
- 4) Non-pharmacological treatment within 3 months of study initiation and during the study period that may affect alcohol consumption
- 5) Current continuous use of antidepressants, opioid analgesics, benzodiazepines, zopiclone, zolpidem, hydroxyzine, alimemazine, propiomazine or other sedatives. (The sporadic use of these compounds is accepted.)
- 6) Any concurrent medication that may affect the results of the trial or is considered to compromise the safety of the participants in the trial. (See SmPCs for possible interactions.)
- 7) Laboratory hepatic values of >3 times the upper limit of the normal range, creatinine clearance <30 ml/min, or other clinically significant abnormalities in the screening laboratory values
- 8) Blood pressure of 180/110 or higher at screening

- 9) Pregnancy, breast-feeding and for premenopausal women, not using one of the contraceptive methods; oral contraceptive, intrauterine contraceptive device (copper or hormonal) or subcutaneous implant.
- 10) Diabetes mellitus type 1 and diabetes mellitus type 2 in need of insulin treatment
- 11) Any current psychiatric or somatic disorder or condition that may affect assessments or compromise participant's safety during the trial
- 12) ASRS- v1.1, part A score ≥4 in the marked cut-off section
- 13) MADRS score ≥ 20
- 14) Current depression that is not mild (mild depression is accepted)
- 15) Suicidality
- 16) Current illicit drug use based on urine-toxicity test and DUDIT
- 17) History of Delirium Tremens or abstinence-induced seizures within 5 years of study initiation
- 18) Epilepsia or seizures other than alcohol-induced, lifetime
- 19) Severe sleep disturbances
- 20) Need of alcohol detoxification
- 21) Living conditions not appropriate to fulfill study requirements
- 22) Use of herbal drugs/tea and supplementations possibly affecting outcome or safety
- 23) Previous participation in this trial or in another trial within 3 months of enrollment into this trial
- 24) Additional factors that render the participant unable to complete the study, as judged by the investigator

4.3. Subject enrolment and randomization

There will be a continuous enrolment of subjects from March 2019 until the PI stops the enrolment phase after decision. Subject eligibility (Visit 1) will be established before treatment randomization (Visit 2). Subjects will be randomized strictly sequentially, as subjects are eligible for randomization. If a subject discontinues from the study, the subject number will not be reused, and the subject will not be allowed to re-enter the study.

4.4. Discontinuation and withdrawal of subjects

The participation in the clinical trial is voluntary and the subjects can decline further participation at any time without providing any motive for the discontinuation. They can also without any given reason at any time demand that their blood and urine samples are destroyed and that their randomization number is removed. If a subject discontinues or is withdrawn from the trial, EoT visit will be performed. In addition, any outcome measures at the ordinary visit that are not covered by the EoT visit will be collected (applicable for visit 4, 6 and 8). AEs will be followed by one (day +7), or if the AEs persists, by two phone calls (day +30).

Withdrawal of subject may take place due to:

- **Incorrect enrolment**

The exclusion criteria (Section 4.2.) apply during the entire study period. Based on the exclusion criteria, subjects will be excluded from the trial before the start of the trial and subjects may also be excluded from the trial and/or study drug during the whole study period

- **Protocol deviations**

The subjects may be withdrawn from the study at the discretion of the investigator if judged non-compliant with study procedures. Subjects will be excluded from the analysis set, if they are no longer judged to fulfill the eligibility criteria; e.g. if the subject has initiated a prohibited medication or other medication not listed or a non-pharmacological treatment considered to compromise the outcome measures in the study. A list of important protocol deviations will be finalized prior to study un-blinding. The number and percentages of

patients with at least one important protocol deviation will be summarized by treatment arm and overall. In addition, the number and percentages of patients within each type of protocol deviation will be provided as well, and a listing of all patients with any important protocol violations/deviations will be provided for the ITT population.

- **Safety Concerns**

If the subject's safety may be compromised, the subject may be withdrawn from the study and/or study drug at the discretion of the Investigator. Subjects must be excluded from treatment in the case of AE where continued treatment, as judged by the Investigator, may compromise the health of the trial subjects. The treatment code must not be broken except in medical emergencies when the appropriate management of the subject necessitates knowledge of the treatment randomization. In case of reporting of AE that may affect the benefit-risk balance, subjects may be unblinded for decision on an abortion of the trial. Subjects will be excluded from the analysis set if an AE considered to affect the assessments and/or the result of the trial is reported, even though subject safety is not compromised. In either case, serious adverse events (SAE) will be followed up.

- **Other reasons for discontinuation**

Subjects lost to follow-up.

[figure not shown]

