Renal and urinary disorders	
Uncommon	Pollakiuria, nocturia
Rare	Glycosuria, polyuria
Reproductive system and breast disorders	
Uncommon	Menorrhagia
Rare	Vaginal discharge, sexual dysfunction
General disorders and administration site conditions	
Common	Chest pain, fatigue
Uncommon	Chest discomfort, influenza like illness, pyrexia, asthenia, malaise
Rare	Feeling cold, cyst
Investigations	
Common	Liver function test abnormal
Rare	Semen analysis abnormal, C-reactive protein increased, blood calcium decreased

* Frequencies are estimated from a post-marketing, observational cohort study

Table 6. Adverse Drug Reactions of Varenicline

Reported adrevers events of varenicline in subjects with AUD

The most prevalent AEs in the varenicline group were nausea (48.1% vs 12.0%), headache (22.1% vs.15.7%) and fatigue (22.1 vs. 10.8%) (de Bejczy et al., 2015). Nausea and abnormal dreams (16.9% vs. 3.6%) were significantly greater in the VAR group compared to placebo (de Bejczy et al., 2015). The AEs that differed significantly between VAR and placebo were nausea (37.1 vs 17.8%), abnormal dreams (27.8% vs. 11.9%) and constipation (9.3% vs 2.0%) (Litten et al., 2013). Compared with placebo, varenicline did not increase suicidal ideation, mood changes or agitation in either study. In sum, the AEs among subjects with AUD are consistent with the side-effects listed in the table above (and ad in SmPC).

Varenicline overdose

No specific antidote for VAR is known. In the event of overdose, hospitalization is advised and management should be as clinically indicated. Hemodialysis may be considered in cases of overdose. No clinically meaningful changes in laboratory test results were observed in the previous clinical trials, nor were there

noteworthy changes in the QT/QTc interval or any other ECG parameter in either preclinical or clinical studies.

Varenicline contraindications

Varenicline is contraindicated in pregnant or nursing women and in patients less than 18 years of age. These are exclusion criteria.

IMP 2: Bupropion Safety Reference Information

Bupropion in AUD population

No controlled clinical trials have assessed BUP in alcohol dependent subjects. However, in the clinical trials assessing combination therapy with VAR and BUP for smoking cessation, alcohol consumption has not been excluded.

Medical risks associated with bupropion

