ANCOVA model will have fixed effects for treatment and center and subject, nicotine use and FHP will be entered as random effect.

Definition of analysis sets

Three analysis sets will be used: Modified Intention-To-Treat (mITT), Per Protocol (PP) and Safety. The primary and secondary efficacy endpoints will be estimated using ITT and PP analysis sets separately. The safety endpoints will be analyzed on the safety analysis set.

1) Modified Intention-to-treat (mITT) analysis set

The mITT analysis set will include all trial subjects who complete screening visit and randomization visit and report that they have taken at least one dose of the randomized IMPs. Subjects will be analyzed according to their randomized IMPs.

2) Per-protocol (PP) analysis set

The PP analysis set constitutes all subjects from the ITT population who are considered to be completers. A completer is defined as a subject who:

- has taken the IMP at least 80% of the planned number of days of the active treatment period
- fulfill the visit milestones, where the visit milestones are met by subjects who have:
 - taken part and completed screening visit, Day 0, Day 21, Day 49 and Day 77
 - successful B-PEth analyses at screening visit, Day 0, Day, 21, Day 49 and Day 77
 - completed TLFB data at screening visit, Day 0, Day, 21, Day 49 and Day 77

In case of violation of any of the above-mentioned criteria the subject will not be included in the PP analysis set for the specific outcome variable. Subjects will be analyzed according to their randomized study drug.

3) Safety set

The safety analysis set includes all subjects who report that they have taken at least one dose of randomized study drug, and for whom any post-dose data is available up until Day 77. Patients will be analyzed according to the actual treatment.

Compliance

Adherence to the study drug regimen will be analyzed by pill count and by plasma levels of IMP1 and IMP2 at visit 4 and visit 6.

Randomization issues

Mistakenly randomizing a subject who does not meet the inclusion/exclusion criteria will be considered a protocol violation. Any such subject will not be included in the analysis sets.

Handling of missing data

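### Section 4.4 excludes randomised subjects from an unnamed analysis set after adverse events or lost eligibility, and no analysis set in section 8.2 carries those rules

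*Protocol*

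**What the plan says.** Section 4.4 contains two exclusions that take effect after randomisation.

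- Rule (a), under Protocol deviations: "Subjects will be excluded from the analysis set, if they are no longer judged to fulfill the eligibility criteria". The examples are starting a prohibited or other unlisted medication, or a non-pharmacological treatment thought to compromise the outcome measures. Section 4.4 also makes the exclusion criteria of section 4.2 apply for the whole study.
- Rule (b), under Safety Concerns: "Subjects will be excluded from the analysis set if an AE considered to affect the assessments and/or the result of the trial is reported". It applies even where the subject's safety is not at issue.

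Section 8.2 defines three sets.

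- mITT: "The mITT analysis set will include all trial subjects who complete screening visit and randomization visit", provided they report at least one dose; they are analysed as randomised.
- PP: "The PP analysis set constitutes all subjects from the ITT population who are considered to be completers". A completer has at least 80% of planned dosing days and meets the visit, B-PEth and TLFB milestones.
- Safety: "The safety analysis set includes all subjects who report that they have taken at least one dose of randomized study drug", with some post-dose data up to Day 77.

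Under Randomization issues, section 8.2 adds a rule for subjects randomised although ineligible: "Any such subject will not be included in the analysis sets".

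**The concern.** Rules (a) and (b) are mandatory, refer to a single set and do not say which one. Section 8.2 has no set to which they belong. Whether a dosed subject with such an event counts in the primary analysis therefore depends on the section the analyst follows.

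The choice matters because the triggers are not independent of treatment or outcome. AE rates differ by arm in the protocol's own safety section. The section 4.2 criteria that stay in force include starting treatment that may affect drinking, a MADRS score of 20 or more, suicidality and need of detoxification; these can reflect poor response or a drug effect. Removing subjects on such grounds breaks the randomised comparison, even if each decision is made blind, because the AE may itself be a consequence of allocation.

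**Working it through.** **Text comparison.** This carries the finding; no figure is needed for it.

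| If the 4.4 rules apply to | Consequence in 8.2 |
|---|---|
| mITT | Contradicts a definition that takes in every subject with both visits and one dose; selects on post-randomisation events |
| PP | Conventional, but the PP definition has neither criterion and is incomplete |
| Safety | Removes subjects whose AEs are to be reported |

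Every reading needs an edit. The only eligibility exclusion in 8.2 concerns status at randomisation, which is a different matter from eligibility lost later.

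**The plan's own allowance.** Section 8.1 plans 380 randomised to reach 360 in mITT and states a loss of about 6.5%. Inflating for that loss gives 360/0.935 = 385.03, so 386, within 3% of 380. The planned numbers themselves allow 380 − 360 = 20 losses, which is 5 per arm of 95 (5.3%), for all reasons.

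**Illustration of a shift.** Inputs from section 7.1: nausea on varenicline vs placebo, 48.1% vs 12.0% in one earlier AUD trial and 37.1% vs 17.8% in the other. Assumptions not in the protocol: a fraction f of nausea cases is removed, and removed subjects differ from those kept by D = 0.5 to 1 SD, in either direction. Each arm mean moves by (fraction removed) × D, so:

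shift in contrast = f × (p1 − p0) × D

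| f | difference 0.361 | difference 0.193 |
|---|---|---|
| 0 | 0 | 0 |
| 0.05 | 0.009–0.018 SD | 0.005–0.010 SD |
| 0.2 | 0.036–0.072 SD | 0.019–0.039 SD |
| 0.5 | 0.090–0.181 SD | 0.048–0.097 SD |

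Section 3.2 expects an effect of d = 0.35 for varenicline. The f = 0.5 row is 26–52% of that (first column) or 14–28% (second); the f = 0.05 row is 3–5% or 1–3%.

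**Illustration against the allowance.** Nausea removals alone would use up 5 losses in a varenicline arm at f = 5/(95 × 0.481) = 0.109 or 5/(95 × 0.371) = 0.142. With the stated 6.5% (95 × 0.065 = 6.2 per arm) the thresholds are 0.135 and 0.175. With the 30% nausea prevalence that section 7.1 also gives, and 5 losses, the threshold is 5/(95 × 0.30) = 0.175.

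**Power.** The stated detectable effects are reproduced by a one-sided 0.025 test: (1.96 + 0.84) × 0.8 × √(2/80) = 0.354 for B-PEth (stated 0.35), and 0.146 for HDD with SD 0.35 and 90 per arm (stated 15%). HDD power at a 15% difference is 82.0%. Removing 10–30% of nausea cases at 48.1% vs 12.0% lowers it to 80.8–78.2%. Lost power is minor; selection is the issue.

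**The case against.** The mITT reading is the weaker one for rule (a). The same paragraph says "a listing of all patients with any important protocol violations/deviations will be provided for the ITT population", which presupposes that deviators remain in that population, and section 8.2 uses ITT loosely for mITT. Section 8.2 also carries TLFB data forward for subjects who drop out, so discontinued subjects are expected to stay in the efficacy analysis. The list of important deviations is finalised before unblinding, and the separate SAP, which was not available here, may name the set. The numerical illustration rests on invented f and D, and nausea is a poor proxy: section 7.1 calls it generally mild or moderate and seldom a cause of discontinuation.

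Much of this is fair. PP is the likelier intention for rule (a), low f is plausible, and the figures show scale, not evidence of bias. What it does not remove is the following. Rule (b) has no pointer to any set. The deviation list is not said to cover it, and its trigger is a judgement with no stated criteria. Blinding does not stop selection through AEs that the drug causes. A SAP could choose a reading, but sections 4.4 and 8.2 would still disagree.

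A further limit applies to any remedy. Withdrawn subjects have an end-of-treatment visit and AE calls but not the remaining visits, and missing B-PEth is not imputed. For B-PEth, the rule therefore matters only for subjects with values between Day 21 and Day 77.

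**Conclusion.** The concern holds. Two binding rules in section 4.4 remove subjects from a set that is not named, and no set in section 8.2 contains them. Confidence is high for this conflict. Bias in the primary comparison is conditional on the rules being applied to mITT; its size and direction cannot be derived from the protocol. On the assumptions shown it runs from zero to about 0.18 SD, and the low end is plausible.

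The rule under Randomization issues is a separate, smaller fault. Read literally, a wrongly randomised subject who took study drug and has post-dose data is left out of the Safety set, contrary to that set's own definition. AEs are still recorded for everyone under section 7.3.1, so this is a gap in safety reporting and not a demonstrated bias by arm.

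This should be fixed before unblinding, because the present wording allows either reading.

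**What to change.** - In section 4.4, state that both exclusion rules apply to the PP set only.
- In section 8.2, add the AE, prohibited-medication or other-treatment, and lost-eligibility criteria to the PP definition, with the list of affected subjects fixed before unblinding.
- State that no subject leaves mITT because of an AE, a medication or treatment started, or eligibility lost after randomisation, and that the data collected under the existing schedule are used.
- Under Randomization issues, keep dosed but wrongly randomised subjects in the Safety set.
- Use one name, mITT, wherever ITT now stands for it.

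The cost is wording in sections 4.4 and 8.2 and the matching SAP text; no visits are added. The drawback is that subjects with confounding medication or treatment stay in the primary set, which may dilute the effect slightly; the amended PP analysis addresses that. The change removes the exclusion by rule but does not recover B-PEth values never collected after an early withdrawal.

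### Section 4.4 removes subjects from an unnamed analysis set after an on-study adverse event, which conflicts with the mITT definition in Section 8.2

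*Protocol*

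**What the plan says.** Section 4.4 has two mandatory removals.

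- Under Safety Concerns: "Subjects will be excluded from the analysis set if an AE considered to affect the assessments and/or the result of the trial is reported". The sentence adds that this holds even where the subject's safety is not at risk.
- Under Protocol deviations: "Subjects will be excluded from the analysis set, if they are no longer judged to fulfill the eligibility criteria". The examples are starting a prohibited drug, or another treatment thought to compromise the outcome measures. The same section says the exclusion criteria remain in force throughout the study.

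Both use the singular for the analysis set and name none. The Protocol deviations paragraph also says that the list of important deviations is finalised before un-blinding and that "a listing of all patients with any important protocol violations/deviations will be provided for the ITT population".

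Section 8.2 defines three sets.

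- mITT: "The mITT analysis set will include all trial subjects who complete screening visit and randomization visit" and who report at least one dose, analysed as randomised.
- PP: "The PP analysis set constitutes all subjects from the ITT population who are considered to be completers". Completers need IMP intake on 80% of planned days plus visit, B-PEth and TLFB milestones.
- Safety: "The safety analysis set includes all subjects who report that they have taken at least one dose of randomized study drug" and who have some post-dose data up to Day 77.

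The only eligibility-based removal in 8.2 is under Randomization issues: "Mistakenly randomizing a subject who does not meet the inclusion/exclusion criteria will be considered a protocol violation". Those subjects are left out of the analysis sets.

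**The concern.** The protocol gives two answers to the question of who is analysed. A SAP that follows either section departs from the other, so this is not a detail left for the SAP to fill in.

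Which set is meant matters. If the adverse-event sentence were applied to mITT, subjects would leave the main efficacy comparison because of something that happened after randomisation and that someone judged to affect the result. Adverse-event rates can differ between active drug and placebo, so the removed fractions can differ too. The arms compared would then no longer be the arms randomised, for B-PEth and for heavy drinking days alike. If the sentence were applied to the safety set, it would remove subjects because of the very event that set is meant to count.

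**Working it through.** **Step 1: set the two sections side by side.** Take a correctly randomised, dosed subject who later has a 4.4 event (an adverse event judged to affect the assessments or result, or eligibility lost on study). Section 4.4 says the subject is out of the analysis set.

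| Set in 8.2 | Entry conditions | On-study AE or lost-eligibility condition | This subject under 8.2 |
|---|---|---|---|
| mITT | Screening and randomisation visits, one reported dose | None | In |
| PP | From ITT; 80% of IMP days; visit, B-PEth and TLFB milestones | None | In only if a completer |
| Safety | One reported dose; post-dose data up to Day 77 | None | In only if such data exist |

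The conflict is unqualified for mITT and conditional for the other two. The Randomization issues rule does not resolve it: it concerns ineligibility at randomisation, not later loss of eligibility, and not adverse events.

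**Step 2: can the context supply the missing name?**

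- *Lost eligibility:* largely yes. A subject removed from the ITT population could not appear in a listing for it (8.2 uses ITT and mITT interchangeably), and deviations are settled before un-blinding. PP is the natural reading, although the PP definition does not contain the rule.
- *Adverse event:* no. The sentence stands under a different heading and has no link to the deviation list or the ITT listing. Because 8.2 estimates efficacy on ITT and PP separately, the singular does not point to one set.
- *Evidence against an mITT reading:* the missing-data rules in 8.2 carry baseline or the last seven days forward for TLFB drop-outs, which presupposes that drop-outs stay in the analysis.

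**Step 3: illustrate the possible shift if the rule were applied to mITT.** The protocol gives no removal rate, so there is no stated figure to reproduce.

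Inputs from the protocol: 360/4 = 90 per arm in mITT (8.1), a hypothesised varenicline effect of 0.35 SD (3.2), and adverse-event rates for varenicline vs placebo from the two earlier trials in AUD (7.1).

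Assumed inputs: a share *s* of 5% to 20% of subjects with the event are judged affected and removed, and removed subjects differ from retained ones by D = 0.5 SD, direction unknown.

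Formula: the removed fraction per arm is f = event rate × *s*. Dropping that fraction moves an arm's mean by f × D, so the contrast moves by D × (f_active − f_placebo).

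| Event, trial | Rates | Gap | Shift at *s* = 5% | Shift at *s* = 20% | As share of 0.35 |
|---|---|---|---|---|---|
| Nausea, US | 37.1% vs 17.8% | 0.193 | 0.5 × 0.193 × 0.05 = 0.005 | 0.5 × 0.193 × 0.20 = 0.019 | 1.4% to 5.5% |
| Nausea, Swedish | 48.1% vs 12.0% | 0.361 | 0.5 × 0.361 × 0.05 = 0.009 | 0.5 × 0.361 × 0.20 = 0.036 | 2.6% to 10.3% |
| Abnormal dreams, Swedish | 16.9% vs 3.6% | 0.133 | 0.5 × 0.133 × 0.05 = 0.003 | 0.5 × 0.133 × 0.20 = 0.013 | about 1% to 4% |

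In subjects per arm, the US nausea rates remove 90 × 0.371 × 0.05 = 1.7 vs 90 × 0.178 × 0.05 = 0.8 at the low end, and 6.7 vs 3.2 at the high end.

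More generally, under the same D, each 10-percentage-point difference in removal between arms shifts the contrast by 0.5 × 0.10 = 0.05 SD.

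**The case against.** The strongest case on the other side has four parts.

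1. *The lost-eligibility sentence is nearly settled by its own paragraph.* This stands. A reader might count it as a contradiction equal to the adverse-event sentence, but the ITT listing and the pre-un-blinding deviation list point to PP. What remains is that neither 4.4 nor the PP definition says so.

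2. *Decisions would be blind anyway.* Section 5.8 keeps the code closed until the last patient is out and a blind analysis is done, Section 9.3 determines deviations before database lock, and 4.4 itself restricts code-breaking. This stands as far as it goes. Blinding guards against deliberate selection, but it does not stop the removed fractions differing by arm when the events themselves do.

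3. *Ordinary nausea or vivid dreams would not trigger the rule.* It needs an event considered to affect the assessments or result. Section 7.1 describes nausea as generally mild or moderate and mostly in the first week, and the primary window is Day 21 to Day 77. Nausea and insomnia also have management rules short of exclusion. This stands, so the rates above are illustration and not a forecast. In addition, B-PEth is not imputed, so a subject with no sample in the window drops out of that analysis whatever 4.4 says.

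4. *The sets are defined in 8.2 and statistical detail is referred to the SAP.* This does not dispose of the point. Section 4.4 is worded as a requirement, and a SAP cannot satisfy both sections.

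**Conclusion.** The point holds in this form: the adverse-event sentence in 4.4 orders removal from an unnamed set, and 8.2 retains the same subject in mITT without qualification, and in PP or safety when their own conditions are met. The lost-eligibility sentence needs the same clarification, although its context already suggests PP.

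A reader might infer three stronger things that the documents do not support.

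- *That the plan will remove adverse-event cases from mITT and so bias the primary results.* The set is not named, and the TLFB imputation rules suggest that drop-outs are kept.
- *That the safety tables will lose adverse-event cases.* All adverse events are recorded (7.3.1) and the safety set is defined by dosing and post-dose data. Nothing indicates that 4.4 was meant to reach it; the wording merely fails to exclude it.
- *That the nausea and dreams rates measure the bias.* The removal share and the 0.5 SD difference are assumed, the direction is unknown, and the Swedish nausea gap is the widest of the contrasts shown. The US rates give about half that shift.

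The size is therefore not known: about 0.005 to 0.019 SD with the US nausea rates, up to 0.036 SD with the Swedish ones, and negligible if few events are so judged. The case for change rests on the contradiction and on keeping the randomised comparison intact, not on these figures. It should be corrected before un-blinding.

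**What to change.** In both sentences of 4.4, name the set. State that an on-study adverse event, a prohibited treatment started or eligibility lost after randomisation may stop study drug or remove a subject from the PP set only, decided blind before un-blinding, and never from the mITT or safety set. Add the matching condition to the PP definition in 8.2.

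The cost is two reworded sentences and one added line. No extra data, visits or subjects are needed.
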